STUDY DESIGN STUDY PROTOCOL AND STATISTICAL ANALYSIS PLAN

[figure not shown]
Evaluation of an Online Intervention to Help LGBTQ Youth Cope With Bullying

NCT: NCT03501264
IRB ID: PRO17060347

Most Recent Renewal: 10/25/2018

STUDY DESIGN

PARTICIPANT TIMELINE

DESCRIPTION OF PARTICIPANT FLOW

1. Advertisements direct potential participants to Screener survey
2. Participants complete screener (in REDCap)
3. If eligible, participants complete informed assent/consent (in REDCap)
 - If ineligible, participants are thanked for their time and no more contact is made with them.
4. If consent is provided, participants are emailed/texted a link to the baseline survey (T1) to complete (in REDCap)
 - Incentive: \$10 when T1 survey is completed
5. Researchers then randomize participants to intervention or control (in REDCap)
6. All participants (both intervention and control groups) receive a list of website resources related to study outcomes.
7. Intervention group receives Intervention Download Instructions (via Redcap)
 - Until participants download the game, email reminders (5 maximum) will be emailed to participants every 3 days (automatically performed in REDCap). If participants also provided a phone number where we can text them, we will remind them via text message to complete the REDCap survey.
8. Participants complete first follow-up survey (T2) (in REDCap)
 - Incentive: \$25 when T2 survey is completed
 - Survey will activate 4 weeks after T1 survey completion
 - Survey will be open until 7 weeks after T1 survey completion
 - All participants will complete survey similar to baseline survey (minus demographics and potential confounder variables)
 - Intervention group will also complete questions about satisfaction with the game.
 - Until participants complete the survey, email reminders (5 maximum) will be emailed to participants every 4 days (automatically performed in REDCap). If participants also provided a phone number where we can text them, we will remind them via text message to complete the REDCap survey.
9. Participants complete second/final follow-up survey (T3) (in REDCap)
 - Incentive: \$50 when T3 survey is completed
 - Survey will activate 8 weeks after T1 survey completion
 - Survey will be open until 11 weeks after T1 survey completion

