We believe our game-based intervention will produce larger and longer-term effects than the above programs because: 1) Our game will utilize more engaging storylines. 2) Prior programs primarily focused on bullying whereas our game also focuses on social and emotional learning (S&EL). S&EL programs build self-management, interpersonal, and problem solving skills, and produce more confident 144 and socially connected 99 youth and such youth report less bullying 105,106. 3) The above games did not address subgroups' needs. We will address experiences of SGM youth (e.g., gay-related shame; fear of "double victimization") 19,145. 4) Our game design and testing are based on state-of-the-art methods 90,146-150. It has been developed by an expert in game-based programs and experts in adolescence, SGM youth, bullying, and game-based programs. 5) The game is informed by an evidence-based logic model ensuring it will attend to behavior change theory and posited mediators.

To our knowledge, this game-based intervention is the:

- First online program targeting SGM youth who are bullying victims, a format that has the potential to reach far greater numbers of SGM youth than traditional face-to-face interventions.
- First bullying prevention program to utilize a gaming format to attract participation and build retention.
- First intervention addressing social and emotional learning with respect to help-seeking among SGM youth.
- First online intervention with 14-18 year olds - as opposed to the typical focus on SGM "youth" who are 18+.

[\[reviewer notes-\]](#)

2.1 Does this research study involve the use or evaluation of a drug, biological, or nutritional (e.g., herbal or dietary) supplement?

* No

[\[reviewer notes-\]](#)

2.2 Will this research use or evaluate the safety and/or effectiveness of one or more devices?

* No

[\[reviewer notes-\]](#)

2.3 Summarize the general classification (e.g., descriptive, experimental) and methodological design (e.g., observational, cross-sectional, longitudinal, randomized, open-label single-blind, double-blind, placebo-controlled, active treatment controlled, parallel arm, cross-over arm) of the proposed research study, as applicable.

Experimental randomized controlled trial

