2.3.1 Does this research study involve a placebo-controlled arm?

* No

[\[reviewer notes-\]](#)

2.4 Will any research subjects be withdrawn from known effective therapy for the purpose of participating in this research study?

* No

[\[reviewer notes-\]](#)

2.5 Will screening procedures (i.e., procedures to determine research subject eligibility) be performed specifically for the purpose of this research study?

* Yes

2.5.1 List the **screening procedures that will be performed for the purpose of this research study. Do NOT include the inclusion/exclusion criteria in this section as they will be addressed in section 3; questions 3.13 and 3.14.**

To determine eligibility, potential participants will complete a brief online screening questionnaire before being entered into this study.

[\[reviewer notes-\]](#)

2.6

Provide a detailed description of all research activities (e.g., all drugs or devices; psychosocial interventions or measures) that will be performed for the purpose of this research study.

This description of activities should be complete and of sufficient detail to permit an assessment of associated risks.

At a minimum the description should include:

- **all research activities**
- **personnel (by role) performing the procedures**
- **location of procedures**
- **duration of procedures**
- **timeline of study procedures**

DESCRIPTION OF PARTICIPANT FLOW

1. Advertisements direct potential participants to Screener survey
2. Participants complete screener (in REDCap)
3. If eligible, participants complete informed assent/consent (in REDCap)
 - o If ineligible, participants are thanked for their time and no more contact is made with them.
4. If consent is provided, participants are emailed/texted a link to the baseline survey (T1) to complete (in REDCap)
 - o Incentive: \$10 when T1 survey is completed
5. Researchers then randomize participants to intervention or control (in REDCap)
6. All participants (both intervention and control groups) receive a list of website resources related to study outcomes. [This document is located in the 'Supporting Documentation Section' of this IRB Protocol.]
7. Intervention group receives Intervention Download Instructions (via Redcap) [This document is located in the 'Supporting Documentation Section' of this IRB Protocol. IRB Reviewers can use this document to download the game.]

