 - o Until participants download the game, email reminders (5 maximum) will be emailed to participants every 3 days (automatically performed in REDCap). If participants also provided a phone number where we can text them, we will remind them via text message to complete the REDCap survey.
8. Participants complete first follow-up survey (T2) (in REDCap)
 - o Incentive: \$25 when T2 survey is completed
 - o Survey will activate 4 weeks after T1 survey completion
 - o Survey will be open until 7 weeks after T1 survey completion
 - o All participants will complete survey similar to baseline survey (minus demographics and potential confounder variables)
 - o Intervention group will also complete questions about satisfaction with the game.
 - o Until participants complete the survey, email reminders (5 maximum) will be emailed to participants every 4 days (automatically performed in REDCap). If participants also provided a phone number where we can text them, we will remind them via text message to complete the REDCap survey.
9. Participants complete second/final follow-up survey (T3) (in REDCap)
 - o Incentive: \$50 when T3 survey is completed
 - o Survey will activate 8 weeks after T1 survey completion
 - o Survey will be open until 11 weeks after T1 survey completion
 - o Until participants complete the survey, email reminders (5 maximum) will be emailed to participants every 4 days (automatically performed in REDCap). If participants also provided a phone number where we can text them, we will remind them via text message to complete the REDCap survey.

2.6.1

Will blood samples be obtained as part of this research study?

* No

*If submitting a protocol for expedited review, it should be clear that the planned blood draws are within the parameters described here:
<http://www.hhs.gov/ohrp/policy/expedited98.html> (see Expedited Research Category #2)

If **Yes**, address the frequency, volume per withdrawal, the total volume per visit, and the qualifications of the individual performing the procedure:

Study Flow Chart:

Name	Modified Date
StudyDesignProcedures_v2_121817.docx	12/18/2017 1:52 PM

[\[reviewer notes-\]](#)

2.7 **Will follow-up procedures be performed specifically for research purposes? Follow-up procedures may include phone calls, interviews, biomedical tests or other monitoring procedures.**

* Yes

Detailed procedures listed in the textbox below:

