Does this research study involve the long-term storage (banking) of biological specimens?

* No

[\[reviewer notes-\]](#)**2.16**

Will research participants be asked to provide information about their family members or acquaintances?

* No

[\[reviewer notes-\]](#)**2.17**

What are the main outcome variables that will be evaluated in this study?

The primary outcomes of this study are related to feasibility. This includes the domains of acceptability, demand, implementation, practicality, integration, adaptation, expansion, and preliminary efficacy testing (based on Bowen, et al., 2009, Am J Prev Med). Below, we present each of the feasibility domains, how they will be measured, and corresponding hypotheses (in parentheses).

ACCEPTABILITY

- Measured using the Gaming Experience Questionnaire (average ≥ 2 in each domain)
- Would you recommend that your friends play this game? ($\geq 75\%$)
- How likely would you be to tell your friends about this game? ($\geq 80\%$)

DEMAND

- The number of hours the game was played ($\geq 75\%$ who played for ≥ 1 hour)
- Intervention group's self-reported use of the game in hours ($\geq 75\%$ who played for ≥ 1 hour)

IMPLEMENTATION

- How many participants in in the intervention arm downloaded the game? ($\geq 80\%$)
- How many people played the game? ($\geq 80\%$)
- How many people completed surveys at T1, T2, T3? ($\geq 80\%$ each survey wave)

- How many people completed ALL surveys? ($\geq 75\%$)
- How many people completed at least 2 surveys? ($\geq 85\%$)
- How many reminders before people completed the surveys? (exploratory)
- How well they did in the game? Did they meet the milestones in the game? (exploratory)
- How many times texted before they completed survey? (exploratory)
- How many times contacted? (exploratory)
- Percent of people who consented post screening (80%)
- How long does it take to get 240 people to enroll in the study? (exploratory)
- Did randomization work? (yes, we hypothesize no group differences in demographics at baseline)
- How many got randomized? (240 participants)
- How many people recruited from which venue? (exploratory)

PRACTICALITY

- How many people have PC or Mac computers in our screening procedures (exploratory)
- Screening based on having an email address (exploratory)
- How easily was the game downloaded without contacting our research coordinator? (exploratory)
- Feelings of safety with regards to password protection? (exploratory)

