- Feelings of safety with regards to having other people see the game? (exploratory)
- Did the game interfere with other activities? (exploratory)

INTEGRATION

- How could this better fit into the youth's life? (exploratory)
- How well does this fit into youth's life now? (exploratory)
- How could the game be improved? (exploratory)

ADAPTATION

- Would you want to be able to play this game on your phone (an app)? (exploratory)
- Did you like this game on the computer? (exploratory)
- This game may not be appropriate for older kids. (how much do they agree with this? Exploratory)
- We will examine the Gaming Experience Questionnaire scores by gender, sexual orientation, race/ethnicity, age (exploratory)

EXPANSION

- How could the game be improved? (exploratory)
- What would you like to be added to the game? (exploratory)
- What would you like removed from the game? (exploratory)

PRELIMINARY EFFICACY TESTING

We hypothesize that the intervention group (versus control group) will have greater levels of change over time in the following outcomes:

1. Increased help-seeking self-efficacy, intentions, and behaviors
2. Increased coping strategies and coping flexibility
3. Increased knowledge and use of online resources
4. Decreased bullying and cyberbullying victimization
5. Decreased loneliness
6. Decreased mental health problems (anxiety, depression, suicidality)
7. Decreased substance use (alcohol, tobacco, and other drugs)
8. Decreased internalized sexual and gender minority stigma

2.18 Describe the statistical approaches that will be used to analyze the study data.

* Addressed below:

For the measures of acceptability, demand, implementation, practicality, integration, adaptation, and expansion, we will report results using descriptive statistics (i.e., percentages and frequencies for categorical variables, or means and standard deviations for continuous variables).

For the preliminary efficacy testing outcomes, we will use repeated measures (i.e., multilevel) statistical models using logistic or linear regression, depending on the distribution

of the outcomes. To examine whether there were greater improvements over time in the intervention group versus control group, we will test the interaction term of time by group. While we are powered to find medium effects (based on Cohen), our primary interest is in estimating the effect size and confidence interval width, which will help us power a future, larger randomized controlled trial.

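### Minor: baseline demographic balance is not a valid sole criterion for the feasibility item on whether randomisation worked

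*Combined protocol and SAP*

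**What the plan says.** The item stands in the implementation list under Main Outcomes and again, in the same words, in section 2.17: "Did randomization work? (yes, we hypothesize no group differences in demographics at baseline". Both lists belong to outcomes that the protocol calls primary. Both are introduced as showing, for each feasibility domain, "how they will be measured, and corresponding hypotheses (in parentheses". The parenthesis is therefore the item's expected result, and it is the only criterion the item has. The neighbouring bullet on the number randomised (240) is a count and does not assess how allocation was done.

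On analysis, section 2.18 says: "For the measures of acceptability, demand, implementation, practicality, integration, adaptation, and expansion, we will report results using descriptive statistics". No test, imbalance threshold or list of variables is given for this item.

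On conduct, step 5 of the participant flow (study design section and section 2.6) says: "Researchers then randomize participants to intervention or control (in REDCap". This follows completion of the T1 survey. Section 3.11 plans 120 participants per arm.

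**The concern.** Whether randomisation worked is a question about conduct: was a proper sequence generated, was it followed, and could anyone foresee or alter an assignment? The plan answers it with a feature of the sample. As written, the rule can err in two ways. It can return a no when allocation was faultless, because chance alone makes the arms differ. It can return a yes when allocation was faulty, because a fault unrelated to demographics leaves demographics balanced.

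This is a rule that can give the wrong answer when followed, and not only a lack of detail. The pilot is meant to inform a larger randomised trial, and whether allocation can be run correctly online is a fair feasibility question for it. The item as worded would report a result that does not answer that question.

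**Working it through.** The plan states no figure for this item, so there is nothing to reproduce. The check asks how often correctly randomised arms would differ, and then what balance can show.

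**Inputs**
- From the plan: 120 per arm (section 3.11). Gender, sexual orientation and race/ethnicity are categorical demographics named in the Adaptation item: "We will examine the Gaming Experience Questionnaire scores by gender, sexual orientation, race/ethnicity, age (exploratory". They are borrowed from there, since the randomisation bullet names no variables.
- Assumed: the category splits, independence between variables, and the cut at which a difference counts. The plan gives none of these.

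**One characteristic held by a proportion p of participants**

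The SD of the between-arm difference in percentage points is 100 × √(2p(1−p)/120).
- p = 0.10: 100 × √(0.18/120) = 3.87 points
- p = 0.50: 100 × √(0.50/120) = 6.45 points

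A gap of 10 points or more is a gap of at least 12 participants. From the exact binomial distribution its probability is 1.3% at p = 0.10, 6.3% at p = 0.20, 8.6% at p = 0.25 and 13.7% at p = 0.50.

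**Three two-category variables, any gap of 10 points or more**
- 80/20 splits: 1 − (1 − 0.0632)³ = 17.8%
- 50/50 splits: 1 − (1 − 0.1375)³ = 35.8%

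**Three four-category variables, at least one category beyond the cut (simulation of correctly randomised trials)**

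| Cut | 60/20/10/10 split | Equal split |
|---|---|---|
| 10 points | about 45% | about 61% |
| 15 points | about 7% | about 10% |
| 20 points | about 0.5% | about 0.5% |

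The rate moves from more than half to almost nothing as the cut moves from 10 to 20 points. Without a stated cut, whoever reads the baseline table decides the answer.

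**The other direction**

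No arithmetic is needed here. T1 holds more than demographics: the T2 survey is described as "All participants will complete survey similar to baseline survey (minus demographics and potential confounder variables", so T1 also carries potential confounders and the content repeated at follow-up. An allocation fault unrelated to demographics, such as a departure from the generated assignments, would not be expected to disturb demographic balance. A table without differences is compatible with both good and faulty conduct.

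**The case against.** The best defence is that the bullet is loose wording with no consequence. It states a hypothesis, not a threshold. The implementation items are reported descriptively. Baseline tables by arm are standard, and nothing downstream uses the answer. Most of this stands, and it is why the point is minor. It does not remove the fault, because the list is presented as how the domains are measured and this item has no other measure.

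A second defence is that balance is not worthless. That also stands: a gross imbalance would be a warning sign. The claim is only that balance is insufficient as the sole criterion.

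A third is that any headline rate of chance differences depends on the cut chosen. That is right, so three cuts are shown and none is put forward as the plan's own.

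A reader might also infer more than the documents support:
- *That baseline significance tests are planned.* Section 2.18 says descriptive statistics, and no test is named.
- *That no group differences means identical counts.* Nothing in the text says so.
- *That allocation was, or would be, steered or alternated.* The documents say that researchers randomise in REDCap. They are silent on whether allocating staff can see T1 answers, and silence is not evidence that they can.
- *That sequence generation and concealment are missing from the study's plan.* They are not described in the text available here, but the listed study flow chart and grant application were not available. The fault in the criterion stands whatever those contain.

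**Conclusion.** The concern holds as a minor point: the stated criterion is wrong as written, in both places. Absence of baseline demographic differences cannot by itself answer whether randomisation worked. It can fail a correct allocation and pass a faulty one.

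The size of the first error cannot be fixed, because the plan sets no cut. The illustrative range of roughly 0.5% to 61% reflects that gap and rests on three independent four-category variables with assumed splits. The second error is a matter of logic and carries no figure.

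A reader might take this as doubt about the trial's randomisation or its efficacy results. The documents do not support that. The time-by-group models, the sample size and the other feasibility thresholds do not depend on this item, and no progression rule is tied to it.

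**What to change.** In both Main Outcomes and section 2.17, remove the yes answer based on balance. Report baseline characteristics by arm descriptively, with no pass/fail reading. Answer the item from the conduct of allocation:

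1. assigned arm against the REDCap-generated allocation (expected 100% match);
2. number of allocations overridden or re-allocated (expected 0);
3. number allocated before T1 completion (expected 0);
4. a statement of how the sequence was generated and whether allocating staff could foresee the next assignment.

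The fourth entry is a description of procedure, and records alone cannot prove it. It is still needed, because the first three could all look clean if assignments were foreseeable.

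The cost is one bullet reworded in two places, one hypothesis dropped, and a small record check on up to 240 participants. This assumes that REDCap holds the generated allocation, the time stamps and any overrides, which the documents do not state. If it does not, the report should say so.

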The prevalence of bullying victimization, health outcomes, and associations between victimization and health outcomes are similar among SGM youth. Further, the needs of SGM youth who are bullied appear to be unique. For example, bullied SGM youth have less access to coping resources. Beyond typical fears of disclosing bullying, SGM youth often fear reactions by school staff and parents due to being SGM 16,17. The gay-related shame many SGM youth internalize 19,20 may make it more likely for them to blame themselves for bullying thus impacting their ability to cope.

We seek to improve health and academic outcomes of SGM youth through a game-based intervention they can easily access. Playing a game is advantageous as SGM youth are often "out" to no or few others off-line 111,112. The game will therefore be accessible to SGM youth who are insufficiently supported in offline programs 60,88,113. The game-based environment is relatively safe for SGM youth to gain coping skills 94,95. Game-based programs about sex 86,87, mental health 114, alcohol use 72-75,115, asthma 116-119, and smoking 76-78 are effective for youth. It is important to note that while face-to-face interventions and game-based interventions incorporating contact with individuals usually, though not always, produce greater effects than "stand-alone" game-based interventions 120-127, our review suggests that "stand-alone" game-based programs produce significant change with respect to various health issues 72-74,76-85,87,128-134. Other advantages of

Section: Section 1 - Objective, Aims, Background and Significance

"stand-alone" game-based interventions are increased fidelity, cost-effectiveness and the ability to reach far larger numbers of individuals 133,135-140.

We chose a game format as 78% of teens play games 141. Games have promoted behavior change in asthma and cancer treatment, and weight control 90,91,93,142. Primary school students who problem solved in virtual situations were more likely to end real-life bullying than controls 3. Grade 7-10 students who experienced cognitive restructuring, graded exposure to and coaching in simulated situations were more likely than controls to stop bullying 4,143. These programs' effects were however moderate and short-term.

1.4 Significance: Why is it important that this research be conducted? What gaps in existing information or knowledge is this research intended to fill?

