Participants will be emailed or texted follow-up surveys immediate post-intervention (time 2; 1 month after baseline survey) and 1-month post-intervention (time 3; 3.5 months after baseline survey). Participants will be reminded up to five times via email/text to complete follow-up surveys.

[\[reviewer notes-\]](#)

2.8 **Does this research study involve the use of any questionnaires, interview or survey instruments?**

* Yes

Upload a copy of all materials except for the SCID or KSADS which are on file at the IRB. The use of all instruments must be addressed in question 2.6 and/or question 2.7 (except for an exempt submission where they should be addressed on the appropriate uploaded exempt form).

Name	Modified Date
T3Survey_v2_121817.docx	2/21/2018 3:02 PM
T2Survey_v2_121817.docx	2/21/2018 3:01 PM
T1Survey_v2_121817.docx	2/21/2018 3:00 PM

Previously the name and publisher for commercially available materials were listed in the textbox below but effective 9/1/2015, all materials (except for the SCID and KSADS) must be uploaded using the Add button above.

[\[reviewer notes-\]](#)

2.9 **If subjects are also patients, will any clinical procedures that are being used for their conventional medical care also be used for research purposes?**

* n/a

If **Yes**, describe the clinical procedures (and, if applicable, their frequency) that will be used for research purposes:

2.10 The blood sample question was moved to 2.6.1.

[\[reviewer notes-\]](#)

2.11 **What is the total duration of the subject's participation in this research study across all visits, including follow-up surveillance?**

* 3 months

[\[reviewer notes-\]](#)

2.12 **Does this research study involve any type of planned deception?**
If Yes, you are required to request an alteration of the informed consent process (question 4.7)

* No

[\[reviewer notes-\]](#)

2.13 **Does this research study involve the use of UPMC/Pitt protected health information that will be de-identified by an IRB approved "honest broker" system?**

* No

[\[reviewer notes-\]](#)**2.14**

Will protected health information from a UPMC/Pitt HIPAA covered entity be accessed for research purposes or will research data be placed in the UPMC/Pitt medical record?

* No

2.14.1

Will protected health information from a non-UPMC/Pitt HIPAA covered entity be obtained for research purposes or will research data be placed in the non-UPMC/Pitt medical record?

* No

[\[reviewer notes-\]](#)**2.15**

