3.8 Does this research study involve neonates of uncertain viability or nonviable neonates?

* No

[\[reviewer notes-\]](#)

3.9 Fetal Tissues: Does this research involve the use of fetal tissues or organs?

* No

[\[reviewer notes-\]](#)

--->

3.10

What is the total number of subjects to be studied at this site, including subjects to be screened for eligibility?

Note: The number below is calculated by summing the data entered in question 3.11. Any additions or changes to the values entered in 3.11 will be reflected in 3.10.

* 480

3.11

Identify each of the disease or condition specific subgroups (include healthy volunteers, if applicable) that will be studied.

Click on the "Add" button and specify for each subgroup:

1) how many subjects will undergo research related procedures at this site; and

2) if applicable, how many subjects will be required to undergo screening procedures (e.g., blood work, EKG, x-rays, etc.) to establish eligibility. Do Not include subjects who will undergo preliminary telephone screening.

*

Subgroup	Number to undergo research procedures	Number to undergo screening procedures
View Control	120	240
View Intervention	120	240

3.12

Provide a statistical justification for the total number of subjects to be enrolled into this research study at the multicenter sites or this site.

* Described below:

This is a feasibility study, which is primarily being conducted to inform a larger randomized controlled trial. For a majority of our outcomes, we are reporting simple descriptive statistics (e.g., how long the game was played by participants). For preliminary efficacy testing, we are primarily interested in effect size and confidence interval estimation; we are NOT necessarily interested in finding statistically significant effects (see Bowen, 2009, Am J Prev Med). Nevertheless, we are powered to find medium effect sizes (based on Cohen, 1988).

[\[reviewer notes-\]](#)**3.13 Inclusion Criteria: List the specific criteria for inclusion of potential subjects.**

- Aged 14 to 18 years old
- English literate
- Lives in the United States
- Identifies as Sexual or Gender Minority
- Has a PC or Mac that is able to download games
- Has an email address
- Has been bullied or cyberbullied in the past 12 months

3.14 Exclusion Criteria: List the specific criteria for exclusion of potential subjects from participation.

- Not bullied or cyberbullied in the past 12 months

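### Does leaving the coding of time and the target contrast unstated in section 2.18 undermine the efficacy effect size?

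*Combined protocol and SAP*

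**What the plan says.** Section 2.18, repeated under Statistical Analysis in the opening design section, says of the efficacy outcomes "we will use repeated measures (i.e., multilevel) statistical models using logistic or linear regression". To compare improvement between arms, it says "we will test the interaction term of time by group". It gives the aim as "our primary interest is in estimating the effect size and confidence interval width", for use in powering a larger trial. Section 3.12 adds that "we are NOT necessarily interested in finding statistically significant effects". None of these places codes time or names a wave as the target.

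On timing, section 2.6 and the opening participant flow open T2 at week 4 and close it at week 7. For T3 they say "Survey will activate 8 weeks after T1 survey completion", closing at week 11. Section 2.7 instead describes T3 as "1-month post-intervention (time 3; 3.5 months after baseline survey". Section 2.11 gives total participation as 3 months.

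**The concern.** With three waves, a group-by-time interaction can mean two things: two contrasts (change to T2 and change to T3) or one slope. A slope combines the waves with weights set by their spacing. At equal spacing with complete data the middle wave gets no weight, and if T3 is much later than T2 the middle wave counts negatively. An early benefit that faded would then be missed or even reversed.

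The protocol leaves room for fading. Section 1.3 says of earlier anti-bullying programs "These programs' effects were however moderate and short-term", although section 1.4 expects "larger and longer-term effects than the above programs". Since the effect size is the stated product of the efficacy analysis, an undefined contrast could send very different numbers into the next sample-size calculation.

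**Working it through.** **Inputs from the documents.** 120 per arm (3.11); at least 80% completion hypothesized at each wave (2.17); weeks 0/4/8 (2.6) or months 0/1/3.5 (2.7).

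**Assumptions.** SD 1, within-person correlation 0.5 with equal correlation between waves, losses at T2 and T3 independent and at random, two-sided 5%, continuous outcome. The plan gives no number for a medium effect; 0.5 SD is assumed.

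**1. The plan's own power statement.** No figure is given to reproduce. For one two-arm contrast at d = 0.5, SE = √(2/120) = 0.129 and power = Φ(0.5/0.129 − 1.96) = 97.2%. With 96 per arm (80% retained) it is 93.4%. The statement is plausible.

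**2. Slope weights, complete data.** Scaled to T1–T3 change, the weight of wave j is t₃(tⱼ − t̄)/Σ(t − t̄)².
- Weeks 0/4/8: t̄ = 4, Σ = 32, giving −1, 0, +1.
- Months 0/1/3.5: t̄ = 1.5, Σ = 6.5, giving −0.81, −0.27, +1.08.

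**3. Slope weights, 80% retention.** The survey patterns are 64% all waves, 16% T1 and T2, 16% T1 and T3, and 4% T1 only. Generalized least squares gives w = (X′MX)⁻¹X′M, where M is the average inverse covariance over these patterns.

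| Schedule | T1 | T2 | T3 |
|---|---|---|---|
| Weeks 0/4/8 | −1.04 | +0.09 | +0.96 |
| Mid-window dates 0/5.5/9.5 | −1.08 | +0.18 | +0.90 |
| Months 0/1/3.5 | −0.88 | −0.17 | +1.05 |

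On the week-based schedule T2 therefore has a small positive weight. It is negative in this table only at 3.5 months. With complete data coded by actual dates, the T2 weight as a share of the T3 weight runs from −17% (weeks 0/4/11) to +67% (0/7/8).

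**4. What the slope estimates, and power (80% retention).** The factor column is the joint 2-df test.

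| Effect at T2, T3 | Linear, 0/4/8 | Linear, 0/1/3.5 | Factor |
|---|---|---|---|
| 0.5, 0 | 0.04; 6% | −0.085; 9% | 95% |
| 0.5, 0.25 | 0.28; 53% | 0.18; 25% | 91% |
| 0.5, 0.5 | 0.52; 96% | 0.44; 89% | 97% |
| 0.25, 0.5 | 0.50; 95% | 0.48; 94% | 91% |

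The 53% in the second row reflects asking about T3. Under factor coding the T3 contrast has a 95% half-width of 0.274, so SE = 0.274/1.96 = 0.140, and its power for 0.25 is Φ(0.25/0.140 − 1.96) ≈ 43%. The slope does no worse than the T3 contrast it approximates.

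**5. Next-trial size in the 0.5-then-0.25 case.** n per arm = 2(1.96 + 0.842)²/d² = 15.70/d² (80% power).
- T2 effect 0.5: 63
- T3 effect 0.25: 252
- Slope at 0/4/8, 0.283: 197
- Slope at 0/1/3.5, 0.177: 501

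The large gap, 63 against 252, is T2 against T3. It exists under factor coding too, until someone chooses the wave.

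**6. Is 3.5 months a live schedule?** The same sentence in 2.7 places T2 at the end of the intervention, 1 month after baseline, and T3 one month after the intervention. One month plus one month is 2 months, matching week 8. Also, 3.5 months is about 15 weeks, after the T3 survey closes at week 11, and it exceeds the 3-month total in 2.11. The week 8 to 11 window is stated twice. The 3.5 is a stray figure.

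**The case for a change.** The strongest reply is that the pilot label excuses nothing, because the estimate is what the efficacy analysis is meant to deliver. In the fading case the possible readings of one dataset give from 63 to about 500 per arm. Two sentences would settle the matter, and an analyst free to choose after seeing the data could pick the kinder contrast.

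Part of this stands. Neither copy of the analysis text fixes the coding or the contrast, and stating both would be tidier. But the upper end of that range uses the 3.5-month figure, which the other timing statements contradict. The rest is mainly the T2-to-T3 difference, which coding alone does not remove. Which wave should size the next trial depends on that trial's own primary time point, which this protocol does not set.

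The power gaps are also weaker than they look. They compare a 2-df test with a slope in scenarios chosen to fade within four weeks. The documents put no duration on the earlier programs' effects, and 3.12 disclaims significance as the aim. If the effect grows linearly, the factor test loses a little: 91% against 95%.

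**Conclusion.** No change follows. The wording in 2.18 is ordinary shorthand that covers a factor interaction as readily as a slope; the linear reading is conjecture. An analyst with three discrete waves and an interest in effect sizes can sensibly report change at T2 and at T3. Under factor coding each would have an expected 95% half-width of about 0.27 SD (0.21 to 0.32 for correlation 0.7 to 0.3). If a single slope were fitted on the week-based schedule, it would be close to the T3-minus-T1 contrast: 0.28 against 0.25 with half fading, and 96% against 97% power if the effect is sustained. That is a legitimate final-follow-up summary, although it would barely register an effect confined to T2.

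The harmful case needs two things together: a linear term and T3 coded at 3.5 months. The second is a slip in 2.7; reconciling it with 2.6 and 2.11 is clerical and alters no result. A joint 2-df test is a preference.

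The figures assume 120 per arm, correlation 0.5, 80% retention with random losses, and a continuous outcome. Logistic models raise the same question on the logit scale, with weights that are not exactly these.
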